2.3 Data Conventions

The data conventions and definitions listed in this section are to be applied to all analyses unless stated otherwise in a subsequent section of this Analysis Plan.

- Data will be analyzed according to the 3 treatment groups, ie, (1) BOTOX 6 U/kg, (2) BOTOX 3 U/kg, and (3) Placebo.
- Concomitant medication and prior medication will be calculated using the following convention: 1) If the stop date of taking medication is prior to injection date, then it will be counted as prior medication; 2) If the start date of taking medication is after or on injection date, then it will be counted as concomitant medication; 3) If the start date of taking medication is prior to injection date and stop date is on or after injection date, then it will be counted as both prior medication and concomitant medication.
- Concurrent procedures are defined as those taken on or after the first injection date.
- All data will be listed with the exceptions of commonly expected results such as physical examination, pregnancy tests results for females when not applicable, etc.
- The level of significance used for all statistical tests will be 0.05. All hypotheses will be tested for statistical significance with 2-sided alternatives.

- Summary statistics of continuous variables will include the sample size (N), mean, standard deviation, median, minimum (Min), and maximum (Max).
- Summary statistics of categorical variables will include the sample size (N) and/or frequency counts and percentages.
- Medical Dictionary for Regulatory Activities (MedDRA) nomenclature will be used to code all adverse events and medical history.
- World Health Organization Drug Dictionary Enhanced (WHO DDE) preferred name and MedDRA will be used to code all medications.
- Metric systems will be used for all applicable measures including (kg), height (cm), and clinical laboratory data (SI: Standard International units).
- Unless otherwise defined, baseline will be the last non-missing value of an analysis variable before treatment. Therefore, in general values collected prior to the treatment on day 1 will be used as baseline except for clinical laboratory tests which will be performed at screening instead of day 1. In the event a variable value is missing at the day 1 before treatment time point, the last non-missing value before day 1 will be used as baseline. Change from baseline is calculated as follow-up minus baseline value.
- Missing values will not be imputed. The multiple imputation (MI) method is only intended for sensitivity analyses of MAS-B scores of the principal muscle group and CGI by Physician.
- Study days from randomization/day 1 will be calculated as:

$$\text{Study days} = \text{visit date} - \text{randomization/day 1 visit date} + 1.$$
- The study day of an event that has occurred before randomization/day 1 will be calculated as:

$$\text{Study day} = \text{date of event} - \text{randomization/day 1 visit date}.$$
- Partial dates occurring when calculation of study day is germane to the study outcome will be handled as follows:
If the year is missing then the date is treated as missing.

If either the month or the day is missing, then the closest date to baseline possible will be used. That is, an event occurring the year before baseline would use December and/or the last day of the month. An event occurring the year after baseline would use January and/or the first day of the month.

All partial dates will be listed “as is” in the data listings.

- All adverse events with missing onset dates will be identified and the missing dates will be imputed as follows for analysis. These imputations are only for assigning adverse events to a particular study phase; calculations such as days to onset will not use these imputations. All partial dates will be listed “as is” in the data listings.
 - (a) For adverse event onset date: If day and month are missing but year is available (..../yy) then the imputed day and month will be 01/01/yy or the injection date if they have the same year, whichever is later. If the day is missing but the month and year are available (mm/../yy), then the imputed day will be mm/01/yy or the injection date if they have the same month and year, whichever is later.
 - (b) For adverse event stop dates: If day and month are missing but year is available (..../yy) then the imputed day and month will be 12/31/yy or the study exit date if they have the same year, whichever is earlier. If day is missing but the month and year are available (mm/../yy), then the imputed day will be the last day of the month mm in the year yy or the study exit date if they have the same month and year, whichever is earlier.
 - (c) If the adverse event onset or stop month, day, and year are missing (..../..), then the study entry date will be used as the adverse event onset date and the exit date will be used as the adverse event stop date.
- Data from unscheduled visits or re-test visits will be treated the same way as scheduled visits, ie, the dates of such visits will be used in the categorization of visit window. The algorithm handling multiple visits within a visit window will also be applied to unscheduled visits and re-test visits.
- For the primary and secondary efficacy analyses where study center is a factor in the analysis model, centers that recruited only a few patients will be pooled together. The following algorithm for pooling study centers will be used:
 - A. Pooling of study centers will by country.
 - B. Within each country, the following will be conducted:

1. Study centers will be ranked in descending order of the total number of patients enrolled.
2. Any center with at least 12 patients will stand on its own.
3. The first center with fewer than 12 patients will be combined with the next smallest center until the total number in the pooled center reaches or exceeds 12 patients.
4. The algorithm of combining centers will continue down the list as described above.
5. If the last pooled center still has less than 12 patients, the last pooled center will be combined with the previous pooled center.

C. If there are less than 12 subjects enrolled in a country, the country will be pooled to the smallest center in the same region (alphabetical order if there is a tie). The regions include Asian Pacific, Europe, and North America. For example, if Canada enrolled less than 12 patients, Canada will be pooled with a smallest center in the United States.

- The mean change from baseline for a given treatment group will be calculated by taking the sum of all individual changes from baseline divided by the number of patients with observations in that treatment group. As a consequence, patients without the particular follow-up data will not be taken into account, except if there is a missing value replacement method used.
- [REDACTED]

3 Disposition and Exit Status

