8.2 Procedures for Final Study Entry

At visit 3 (randomization) patients must meet all of the inclusion criteria and must not meet any of the exclusion criteria. Also, all females of childbearing potential must have a negative urine pregnancy test.

The patient is considered to have entered this study at the time of randomization to treatment on day 1. See Section 5.5 for the method for assignment to treatment groups/randomization.

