2.2 Treatment Visits

All days are referenced to day 1. Day 1 is the randomization/treatment day. In the cases where randomization and treatment happened on different days, the day of treatment will be used as day 1. Visits according to the windows below will be determined for each variable analyzed unless noted otherwise in the following sections. If there are values from multiple visits in a given window, the value collected from the visit closest to the target day will be used to represent the window. If 2 visits with values fall within the same window and are equidistant from the target day, the value from the first of the 2 visits chronologically will be used to represent the window. For clinical laboratory variables, the last non-missing observation for that visit window

will be used. This rule will be applied separately for each variable for non-missing data only. (The exception is because re-runs of laboratory variables may only involve one or a few variables and would thus include missing data for many variables).

Visit	Target Day of the Visit	Visit Window (Day*)
Screening	-28	\leq Day -1
Day 1 (Randomization/Treatment)	1	Day 1
Week 2	15	Day 2 to Day 22
Week 4	29	Day 23 to Day 36
Week 6	43	Day 37 to Day 50
Week 8	57	Day 51 to Day 71
Week 12	85	\geq Day 72

* All days are referenced to day 1. For post-treatment visits, study day = visit date – day 1 date+1 while for pre-treatment visits, study day = visit date - day 1 date.

The visit windows will be used for by-visit analyses in both modified intent-to-treat (mITT) and safety population analyses.

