6.2 Treatment Emergent Adverse Events

Adverse events are collected both for the screening/baseline period prior to treatment (which are referred to as pre-treatment adverse events as cited in Section 4.6) and for the follow-up period after treatment is initiated.

A treatment-emergent adverse event (TEAE) is a post-baseline adverse event with onset after the initiation of study treatment or an adverse event with onset prior to study treatment that worsened in severity or became serious after the initiation of study treatment. The number and percentage of patients reporting each event will be summarized and presented for all events and tabulated by treatment groups (6 U/kg, 3 U/kg, and placebo) and overall as follows:

- i. By primary SOC and preferred term. At each level of summarization (overall, primary SOC, and preferred term) a patient will be counted once if he/she reports 1 or more experiences at that level.

- ii. By primary SOC, preferred term and severity. For a given adverse event of a patient, if more than 1 severity grade was reported, the worst severity grade will be included in the tabulation.

All treatment-related TEAEs (study drug-related and injection procedure-related TEAE) will be presented by primary SOC and preferred term. A listing of adverse events leading to discontinuation will also be provided.

The number and percentage of patients with any of the preferred terms will be summarized for each primary SOC and preferred term. All patients will be counted only once for each preferred term when multiple occurrences of the same preferred term are reported.

In addition, individual patient data listings (including adverse event listings that include the investigator verbatim terms and MedDRA lower level terms) will be provided.

Furthermore, the assessment of possible distant spread of toxin will be performed using the list of 39 MedDRA preferred terms (version 19.0 or its updated version as appropriate during the time of data analysis).

MedDRA Preferred Terms Evaluated for Possible Distant Spread of Toxin

Cardiac Disorders

Bradycardia

Eye Disorders

Accommodation disorder
Diplopia
Extraocular muscles paresis
Eyelid function disorder
Eyelid ptosis
Pupillary reflex impaired
Vision blurred

Gastrointestinal Disorders

Constipation
Dry mouth
Dysphagia
Ileus paralytic

Infections and Infestations

Botulism

Musculoskeletal and Connective Tissue Disorders

Muscular weakness

Nervous System Disorders

Bulbar palsy

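### The adverse-event onset imputation in SAP 2.3 never checks the stop date, so an event that ended before injection can be dated after its own end and assigned to the wrong study phase

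*SAP*

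**What the plan says.** SAP 2.3 (Data Conventions) gives three rules for incomplete adverse-event dates.

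- Rule (a), onset with only the day missing: "the imputed day will be mm/01/yy or the injection date if they have the same month and year, whichever is later". With day and month missing: "then the imputed day and month will be 01/01/yy or the injection date if they have the same year, whichever is later".
- Rule (b), partial stop dates, for example with the day missing: "the imputed day will be the last day of the month mm in the year yy or the study exit date", taking the earlier where the month and year agree with the exit date. It fills gaps in the stop date and does not refer back to onset.
- Rule (c), date wholly missing: "then the study entry date will be used as the adverse event onset date", and the exit date serves as the stop date. Protocol 8.2 defines entry: "The patient is considered to have entered this study at the time of randomization to treatment on day 1".

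The purpose is stated too: "These imputations are only for assigning adverse events to a particular study phase".

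The phases are defined elsewhere. SAP 6.2 says that a treatment-emergent event "is a post-baseline adverse event with onset after the initiation of study treatment", or an earlier event that later worsened or became serious. SAP 4.6 defines pre-treatment events by onset between consent and day 1, or by worsening of medical history in that interval. Neither section has a condition on the stop date.

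**The concern.** Protocol 9.1.1 collects adverse events from informed consent, and Protocol 8.3.1 places screening 2 to 4 weeks before day 1. An event can therefore start and resolve before any study drug is given. If its stop date is known, its phase is known, however vague its onset. Rule (a) discards that information and moves the onset to the injection date. Rule (c) has the same gap when the onset is wholly missing.

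At stake is the content of the safety tables. An event known to precede the drug could appear among the treatment-emergent events. The distant-spread list in SAP 6.2 contains non-specific terms such as constipation and dyspnoea, so it could be affected as well. The same event would be missing from the pre-treatment listing.

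**Working it through.** The plan states no figure to reproduce, so the check applies the rules as written.

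**Step 1. What rule (a) returns.** Let I be the injection date. If the onset month and year match those of I, the imputed onset is max(first of month, I) = I, because I cannot fall before the first of its own month. If only the year is known and it matches, the imputed onset is max(1 January, I) = I. The stop date does not enter either expression.

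**Step 2. Worked cases**, with an illustrative injection on 20 June 2016:

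| Recorded onset | Recorded stop | Onset under the SAP | Phase under the SAP | Phase with a stop-date check |
|---|---|---|---|---|
| June 2016, day missing | 10 June | 20 June, 10 days after stop | treatment-emergent | pre-treatment |
| 2016, day and month missing | 10 June | 20 June, 10 days after stop | treatment-emergent | pre-treatment |
| May 2016, day missing | 10 June | 1 May | pre-treatment | pre-treatment |
| June 2016, day missing | 25 June | 20 June | treatment-emergent | treatment-emergent |

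Only the first two rows go wrong. Under rule (c), a wholly missing onset with a stop of 10 June gets the entry date, day 1, which is again after the stop.

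**Step 3. How often the rule misfires when it can.** Take events that began and ended within a screening period of L days: onset a days and stop b days before injection, with 1 ≤ b ≤ a ≤ L. There are L(L+1)/2 such pairs. If injection falls on day d of the month, the onset lies in the same month when a ≤ m, where m = min(d−1, L). That is m(m+1)/2 pairs. The share moved to the injection date is therefore the mean over d of m(m+1) / [L(L+1)].

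For L = 28 and a 30-day month, the sum of m(m+1) over d = 1 to 29 is 28×29×30/3 = 8,120. Day 30 adds 28×29 = 812. The share is 8,932 / (30×812) = 0.37. Full enumeration over every injection date in 2016 gives:

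| Screening length | Day missing | Day and month missing |
|---|---|---|
| 14 days | 68% | 97% |
| 21 days | 53% | 96% |
| 28 days | 38% | 95% |

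In every affected day-missing case the imputed onset was later than the stop date. These percentages weight all date pairs equally. They describe only events that began and ended in screening and have an incomplete onset.

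**Step 4. From share to count.** The count would be the number of such events times the share above. The documents give neither the number of adverse events nor the frequency of incomplete dates, so no count can be calculated.

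**The case against.** The strongest reply is that moving an uncertain onset to the injection date is a normal conservative convention. It is, when the stop date is unknown or falls on or after injection. When the stop date is before injection, the phase is not in doubt and there is nothing to be conservative about.

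A second reply is that the definition in SAP 6.2 already excludes these events: they are not naturally post-baseline, and an onset on the injection day is not clearly after the start of treatment. The wording is indeed ambiguous for same-day onsets. But the imputation exists to assign phase, and choosing the later date has a purpose only if that date counts as post-treatment. An onset after the event's own end is wrong on either reading.

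A third reply stands as a limit on size. Sites ask about adverse events at screening and again on day 1 before treatment, so incomplete dates in so short a period should be uncommon. Partial dates are also listed as recorded, so an anomaly would be visible in the listings, though not in the tables.

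Three stronger readings are tempting, and the documents do not support them.

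- A reader might infer that rule (c) also loses treatment-emergent events, because entry is tied to randomization and injection could come later. But Protocol 8.2 ties entry to day 1, Protocol 8.3.3 puts randomization and injection in one visit, and SAP 2.2 says: "In the cases where randomization and treatment happened on different days, the day of treatment will be used as day 1". Read together, entry is the treatment day.
- A reader might take about half as the error rate, since (0+1+…+28+28)/(28×30) = 434/840 = 0.52 of the days in a 28-day screening period fall in the injection month. That is a share of days. It includes events still ongoing at injection, which the rule handles acceptably.
- A reader might infer that differences between arms are materially diluted. The rule is the same in all arms, the adverse-event tables are descriptive with no between-arm test specified, and a few events would have a negligible effect.

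**Conclusion.** The point holds as a narrow defect. Followed literally, rules (a) and (c) give an event that ended before injection an onset after its own end, and such an event could be counted as treatment-emergent. No safeguard against this was found elsewhere in the SAP or the protocol.

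It requires an onset that is wholly missing, or partial and matching the injection's month and year (or its year, if only that is known), together with a stop date before injection. Events with a complete onset, or a known onset month before the injection month, are classified correctly. The conclusion on phase assumes that an onset dated on the injection day counts as post-treatment; the date inconsistency does not depend on that. Rule (c) is read as replacing only the date that is missing.

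The documents do not show that such records exist, so the tables could contain these events; it cannot be said that they will. The number is probably small, no particular safety conclusion can be shown to change, and efficacy and power are untouched. This is a desirable correction of low severity.

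**What to change.** Add one sentence to rules (a) and (c) of SAP 2.3: *If the stop date (recorded, or imputed under (b) from a partial date) is before the injection date, the event is assigned to the pre-treatment phase, and an imputed onset is never later than the stop date; otherwise the rules apply unchanged.*

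Using a stop date imputed under (b) is safe here. Rule (b) takes the latest date compatible with what was recorded, capped at study exit, so if that date precedes injection the event had ended by then. The phase should be assigned directly, because the first of the month or 1 January may fall before consent and so outside the interval in SAP 4.6.

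SAP 2.3 already applies this logic to medications: one stopped before injection is classed as prior. The cost is one sentence and a line of code. No new data are needed, and no efficacy result changes.

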3.1 Screening Log Data

The number of subjects who are screen failures versus those who are qualified will be tabulated. The characteristics (sex, race, and age) of the failed and qualified subjects will be summarized. In addition, reasons for failure will be tabulated by “inclusion” and “exclusion”. The screen failures will be listed by site.

3.2 Disposition and Exit Status

A patient disposition and exit status table will be done for the all randomized subjects population. A cumulative frequency table showing patient disposition (enrolled, completed, and discontinued) in the study with sub-categorization by reason for premature discontinuation for each treatment group will be generated.

4

Demographics and Other Baseline Characteristics

4.1

Demographics

The demographics will be summarized for the mITT population.

Age, race, sex will be summarized using frequency tabulations and/or summary statistics, both by treatment group and overall patients. Race will be classified as Caucasian and non-Caucasian (black, Asian, Hispanic, and other). In addition, race will be displayed as collected in the case report form (Caucasian, black, Asian, Hispanic, and other).

4.2

Disease Characteristics

For the mITT population, the MAS-B score at baseline, the history of disease including the type (monoplegic, hemiplegic, or triplegic), etiology (cerebral palsy or post-stroke), previous botulinum toxin exposure status, onset, and duration will be summarized by treatment group for the mITT population.

4.3

Prior Medications

Using the mITT population, the number and percent of patients who had taken prior medication (as defined in Section 2.3) will be presented by treatment group for the base preferred (drug) name according to the World Health Organization Drug Dictionary Enhanced (WHO DDE) with the same active ingredients by the primary system organ class (SOC) and preferred term of the MedDRA code.

4.4

Concomitant Medications and Concurrent Procedures

Concomitant medications (as defined in Section 2.3) will be presented by WHO DDE preferred drug name for each treatment group by the primary SOC and preferred term of the MedDRA code using the mITT population. Concurrent procedures will be listed for the mITT population.

4.5

Medical History

Data for medical history with onset dates prior to the initial informed consent form signed date will be tabulated and presented by the SOC and preferred term of MedDRA code for each treatment group using the mITT population.

4.6 Pre-treatment Adverse Events

Data for pre-treatment adverse events, adverse events with onset date in-between informed consent date and randomization/day 1 visit or medical history that worsened duration this period will be listed.

4.7 Pre-treatment Serious Adverse Events

All pre-treatment serious adverse events will be flagged in the pre-treatment adverse events listing.

5 Efficacy Analyses

The primary, secondary, and other efficacy endpoints are listed below. The efficacy analysis for US FDA is described in Section [10](#).

Primary efficacy endpoints:

- The average change from baseline in MAS-B score of principal muscle group at weeks 4 and 6
- The average CGI by Physician at weeks 4 and 6 (co-primary efficacy endpoint for US FDA only)

Secondary efficacy endpoints:

- The average CGI by Physician at weeks 4 and 6 (for non-US FDA analyses)
- The average change from baseline in MAS-B of the finger flexor muscle group at weeks 4 and 6
- Goal Attainment Scale (GAS) by Physician at weeks 8 and 12
- Modified Tardieu Scale (MTS) of the principal muscle group

[REDACTED]

| [REDACTED]

| [REDACTED]

- [REDACTED]
- [REDACTED]
- [REDACTED]

